2.2.2. Secondary Estimands

For the purposes of the study, the following also applies to the tertiary/exploratory estimands:

• Seroconversion is defined as an HAI titer <1:10 prior to vaccination and ≥1:40 at the time point of interest, or an HAI titer ≥1:10 prior to vaccination with a 4-fold rise at the time point of interest.

The secondary estimands for the secondary objective will use the hypothetical strategies from the EMA ICH E9 (R1) addendum¹ and estimate the immune response.

2.2.2.1. HAI Titers for Each Strain Targeted by the Study Vaccine for Each Strain 2.2.2.1.1. Participants From 65 Through 85 Years of Age

• HAI GMTs before Vaccination 1, prior to Vaccination 2 (Day 21, if applicable), and at 1, 4, and 8 weeks after the last vaccination.

This estimand includes the following attributes:

- Treatment: 1-Visit schedules or 2-visit schedules with modRNA, licensed QIV, and/or placebo or their combinations as listed in Table 2.
- Population: Evaluable immunogenicity population as defined in Section 4.
- Variable: HAI GMTs on Day 1 prior to Vaccination 1, prior to Vaccination 2 (Day 21, if applicable), and at 1, 4, and 8 weeks after the last vaccination.
- Intercurrent event(s): For participants who discontinue, have major protocol violations, and/or results obtained from out-of-window blood draws. The windows of blood draws, as mentioned throughout the SAP, refer to the assay windows defined in Section 4 in this SAP.
- Population-level summary: HAI GMTs and associated 2-sided 95% CI for each strain from before Vaccination 1, prior to Vaccination 2 (Day 21, if applicable), and at 1, 4, and 8 weeks after receipt of Vaccination 2.
- HAI GMFRs from before Vaccination 1 to prior to Vaccination 2 (Day 21, if applicable) and to 1, 4, and 8 weeks after receipt of the last vaccination.

- Treatment: 1-Visit schedules or 2-visit schedules with modRNA, licensed QIV, and/or placebo or their combinations as listed in Table 2.
- Population: Evaluable immunogenicity population as defined in Section 4.
- Variable: GMFRs from before Vaccination 1 to prior to Vaccination 2 (Day 21, if applicable) and to 1, 4, and 8 weeks after receipt of the last vaccination.
- Intercurrent event(s): For participants who discontinue, have major protocol violations, and/or results obtained from out-of-window blood draws.

- Population-level summary: HAI GMFRs and associated 2-sided 95% CI for each strain from before Vaccination 1 to prior to Vaccination 2 (Day 21, if applicable) and to 1, 4, and 8 weeks after the last vaccination.
- The proportion of participants achieving HAI seroconversion for each strain prior to Vaccination 2 (Day 21, if applicable) and at 1, 4, and 8 weeks after receipt of the last vaccination.

This estimand includes the following attributes:

- Treatment: 1-Visit schedules or 2-visit schedules with modRNA, licensed QIV, and/or placebo or their combinations as listed in Table 2.
- Population: Evaluable immunogenicity population as defined in Section 4.
- Variable: Presence of participants achieving HAI seroconversion for each strain prior to Vaccination 2 (Day 21, if applicable) and at 1, 4, and 8 weeks after receipt of the last vaccination.
- Intercurrent event(s): For participants who discontinue, have major protocol violations, and/or results obtained from out-of-window blood draws.
- Population-level summary: The proportion of participants achieving HAI seroconversion for each strain and associated 2-sided 95% CIs, by vaccine group, prior to Vaccination 2 (Day 21, if applicable) and at 1, 4, and 8 weeks after receipt of the last vaccination.
- The proportion of participants with HAI titers ≥1:40 for each strain before Vaccination 1, before Vaccination 2 (Day 21, if applicable), and at 1, 4, and 8 weeks after receipt of the last vaccination.

- Treatment: 1-Visit schedules or 2-visit schedules with modRNA, licensed QIV, and/or placebo or their combinations as listed in Table 2.
- Population: Evaluable immunogenicity population as defined in Section 4.
- Variable: Presence of participants with HAI titers ≥1:40 for each strain before Vaccination 1, before Vaccination 2 (Day 21, if applicable), and at 1, 4, and 8 weeks after receipt of the last vaccination.
- Intercurrent event(s): For participants who discontinue, have major protocol violations, and/or results obtained from out-of-window blood draws.

• Population-level summary: The proportion of participants with HAI titers ≥1:40 for each strain and associated 2-sided 95% CIs, by vaccine group, before Vaccination 1, before Vaccination 2 (Day 21, if applicable), and at 1, 4, and 8 weeks after receipt of the last vaccination.

2.2.2.1.2. Participants From 18 Through 64 Years of Age

In participants from 18 through 64 years of age, the estimands will be defined and analyzed similarly as above. The time points will be adjusted to 1, 4, and 8 weeks after receipt of vaccination. The baseline will be before vaccination.

2.2.2.2. HAI Titers for Each Strain Targeted by the Study Vaccine for All Strains 2.2.2.2.1. Participants From 65 Through 85 Years of Age

- In participants from 65 through 85 years of age, the following estimands are for those who have received at least 1 dose of a quadrivalent vaccine.
- The proportion of participants achieving HAI seroconversion for all strains prior to Vaccination 2 (Day 21, if applicable) and at 1, 4, and 8 weeks after receipt of the last vaccination.

- Treatment: 1-Visit schedules or 2-visit schedules with modRNA, licensed QIV, and/or placebo or their combinations as listed in Table 2.
- Population: Evaluable immunogenicity population as defined in Section 4.
- Variable: Presence of achieving HAI seroconversion for all strains prior to Vaccination 2 (Day 21, if applicable) and at 1, 4, and 8 weeks after receipt of the last vaccination.
- Intercurrent event(s): For participants who discontinue, have major protocol violations, and/or results obtained from out-of-window blood draws.
- Population-level summary: The proportion of participants achieving HAI seroconversion for all strains (targeted by the study vaccine) and associated 2-sided 95% CIs, by vaccine group, prior to Vaccination 2 (Day 21, if applicable) and at 1, 4, and 8 weeks after receipt of the last vaccination.
- The proportion of participants with HAI titers ≥1:40 for all strains before Vaccination 1, before Vaccination 2 (Day 21, if applicable), and at 1, 4, and 8 weeks after receipt of the last vaccination.

[figure not shown]
This estimand includes the following attributes:

- Treatment: 1-Visit schedules or 2-visit schedules with modRNA, licensed QIV, and/or placebo or their combinations as listed in Table 2.
- Population: Evaluable immunogenicity population as defined in Section 4.
- Variable: Presence of participants with HAI titers ≥1:40 for all strains before Vaccination 1, before Vaccination 2 (Day 21, if applicable), and at 1, 4, and 8 weeks after receipt of the last vaccination.
- Intercurrent event(s): For participants who discontinue, have major protocol violations, and/or results obtained from out-of-window blood draws.
- Population-level summary: The proportion of participants with HAI titers ≥1:40 for all strains and associated 2-sided 95% CIs, by vaccine group, before Vaccination 1, prior to Vaccination 2 (Day 21, if applicable), and at 1, 4, and 8 weeks after the last vaccination.

[figure not shown]
2.2.2.2. Participants From 18 Through 64 Years of Age

In participants from 18 through 64 years of age, the estimands will be defined and analyzed similarly as above. The time points will be adjusted to 1, 4, and 8 weeks after receipt of vaccination. The baseline will be before vaccination.

[figure not shown]
2.2.3. Tertiary/Exploratory Estimands

[figure not shown]

2.3. Study Design

2.3.1. Overall Design

This is a Phase 1/2 randomized, single-blinded (sponsor-unblinded) study to evaluate the safety, tolerability, and immunogenicity of a modRNA vaccine against influenza in healthy individuals from 18 through 85 years of age.

In participants from 65 through 85 years of age:

Participants will be randomized to and will be blinded to which 1-visit or 2-visit vaccination schedules they will receive:

2-Visit Schedules

- 2 Doses of qIRV encoding 2 A strains and 2 B strains at a dose level of CCl
 administered 21 days apart
- 2 Doses of licensed QIV, administered 21 days apart (as a control group)
- A dose of licensed QIV following by a dose of bIRV encoding 2 A strains at a dose level of either CCl administered 21 days apart

1-Visit Schedules

- A dose of licensed QIV administered concurrently in the opposite arm with bIRV encoding 2 A strains at a dose level of either CC
- A dose of bIRV encoding 2 A strains at a dose level of CCl administered concurrently in the opposite arm with bIRV-encoding 2 B strains at a dose level of CCl
- A dose of qIRV encoding 2 A strains and 2 B strains at the following dose level combinations:

• A dose of licensed QIV (as a control group)

Substudy B enrollment will be separated into an initial and expanded enrollment. Depending on the availability of study intervention and operational prioritization, groups in Substudy B may not all be randomized concurrently; however, a minimum of 2 groups will be open for randomization at any 1 time.

During initial enrollment, each group (vaccine formulation/dose level, or control) will comprise 15 participants. Hence, Substudy B initial enrollment will comprise approximately 165 participants.

Substudy B expanded enrollment will comprise group(s) of 120 participants following the vaccination schedule(s) as selected by the sponsor's IRC from initial enrollment. If deemed acceptable, an additional 120 participants will be enrolled in that group (expanded enrollment). Additionally,

- Expanded-enrollment groups may also be included that comprise only the first dose from 2-visit—schedule initial-enrollment groups, eg, 1 dose of qIRV at a dose level of CCI.
- A control group of 120 participants will be enrolled during expanded enrollment who will receive a dose of licensed QIV followed by placebo, administered 21 days apart.

In participants from 18 through 64 years of age:

Participants will be randomized to and will be blinded to two 1-visit schedules:

- A dose of qIRV encoding 2 A strains and 2 B strains at a dose level of CCI
- A dose of qIRV encoding 2 A strains and 2 B strains at a dose level of CCI

Two hundred forty participants will be randomized in a 1:1 ratio to 1 of the 2 above vaccination groups.

Therefore, Substudy B will consist of approximately 645 to 1725 participants, depending on the number of groups selected to progress to expanded enrollment.

Dose levels detailed above are summarized in Table 2.

Vaccine Doses En	ncoding HA for Ea	ch Strain					
Initial Enrollment (Participants From 65 Through 85 Years of Age)		Expanded Enrollment					
		2				Vaccination 2	
Left Deitold	Right Deitoid	Deltoid	_			Left Deltoid	
	qIRV CC		a	Participants	qIRV CCI		
	2 x A, 2 x B			from 18 through	2 x A, 2 x B		
	bIRV CCI 2 x A CCI			64 years of age	qIRV CC 2 x A, 2 x B		
	bIRV CCI 2 x A CCI			Participants from	Licensed QIV ^b	Placebo	
	Licensed OIV			65 through	Other vaccine group(s) as selected		
Licensed QIV	Zironiou Qi v			•	the sponsor's IRC from initial enrollment for expanded enrollment Expanded-enrollment groups may a		
,				age			
Licensed QIV							
						C 1	
bIRV CC							
2 x A							
	(Participants From (N = 15 per groon 1 Left Deltoid Licensed QIV Licensed QIV birv CC	(Participants From 65 Through 85 Years of (N = 15 per group) on 1	(N = 15 per group) on 1 Vaccination 2 Right Deltoid QIRV CCI 2 x A, 2 x B CCI bIRV CCI 2 x A CCI Licensed QIV Licensed QIV Licensed QIV bIRV CCI 2 x A CCI Licensed QIV	(Participants From 65 Through 85 Years of Age) (N = 15 per group) on 1 Vaccination 2 Left Deltoid QIRV 2 x A, 2 x B CCI bIRV CCI 2 x A CCI Licensed QIV Licensed QIV Licensed QIV bIRV CCI 2 x A CCI 2 x A CCI Licensed QIV	(Participants From 65 Through 85 Years of Age) (N = 15 per group) on 1 Left Deltoid QIRV 2 x A, 2 x B CCI bIRV 2 x A CCI Licensed QIV Licensed QIV Licensed QIV BIRV CCI 2 x A CCI Licensed QIV Licensed QIV Licensed QIV BIRV CCI 2 x A CCI Licensed QIV Licensed QIV Licensed QIV	Carticipants From 65 Through 85 Years of Age) (N = 15 per group)	

a. Safety and immunogenicity data accumulated at least 1 week following the last vaccination in each group will be reviewed and, if the data are deemed acceptable, an additional 120 participants will be enrolled in that group (expanded enrollment).

b. At the discretion of the sponsor's IRC, a control group of 120 participants may be enrolled during the expanded enrollment who will receive a dose of licensed QIV followed by placebo, administered 21 days apart.

3. ENDPOINTS AND BASELINE VARIABLES: DEFINITIONS AND CONVENTIONS

3.1. Primary Endpoints

3.1.1. Primary Safety Endpoints

All participants will be asked to monitor and record local reactions, systemic events, and use of antipyretic medication for 7 days from the day of administration of each vaccination. These prospectively self-collected occurrences of local reactions and systemic events will be graded. The grading scales used in this study to assess local reactions and systemic events as described below are derived from the FDA CBER guidelines on toxicity grading scales for healthy adult volunteers enrolled in preventive vaccine clinical trials.² Below are the primary safety endpoints for local reactions and systemic events:

- Local reactions (pain at the injection site, redness, and swelling) within 7 days after each vaccination in each vaccine group.
- Systemic events (fever, fatigue, headache, chills, vomiting, diarrhea, new or worsened muscle pain, and new or worsened joint pain) within 7 days after each vaccination in each vaccine group.

For all participants randomized and receiving at least 1 dose of study intervention, below are the primary safety endpoints for AEs and SAEs:

- AEs from the first vaccination through 4 weeks after the last vaccination.
- SAEs from the first vaccination through 6 months after the last vaccination.

3.1.1.1. Local Reactions

During the reactogenicity e-diary reporting period, participants will be asked to assess redness, swelling, and pain at the injection site and to record the symptoms in the reactogenicity e-diary. Local reactions will be assessed at the injection site on the right arm only.

If a local reaction persists beyond the end of the reactogenicity e-diary period following each vaccination, the participant will be requested to report that information. The investigator will enter this additional information in the CRF.

Redness and swelling will be measured and recorded in measuring device units (range: 1 to 21) and then categorized during analysis as absent, mild, moderate, or severe based on the grading scale in Table 3. Measuring device units can be converted to centimeters according to the following formula: 1 measuring device unit = 0.5 cm. Pain at the injection site will be assessed by the participant as absent, mild, moderate, or severe according to the grading scale in Table 3.

	Mild (Grade 1)	Moderate (Grade 2)	Severe (Grade 3)	Potentially Life-Threatening (Grade 4)
Pain at the injection site	Does not interfere with activity	Interferes with activity	Prevents daily activity	Emergency room visit or hospitalization for severe pain
Redness	>2.0 cm to 5.0 cm (5 to 10 measuring device units)	>5.0 cm to 10.0 cm (11 to 20 measuring device units)	>10 cm (≥21 measuring device units)	Necrosis or exfoliative dermatitis
Swelling	>2.0 cm to 5.0 cm (5 to 10 measuring device units)	>5.0 cm to 10.0 cm (11 to 20 measuring device units)	>10 cm (≥21 measuring device units)	Necrosis

Presence or Absence

For the data summary of the presence (yes or no) of a local reaction during the interval from Day 1 through Day 7 for each dose, where Day 1 is the day of each dose, the following variables are required in order to compute the proportions:

- Presence (yes or no) of each severe/Grade 4 local reaction on each day and any day (Day 1 through Day 7);
- Presence (yes or no) of each local reaction by maximum severity on any day (Day 1 through Day 7).

For each local reaction and any local reaction on any day, Table 4 details the algorithm to derive the presence of a reaction (yes or no) during the interval from Day 1 through Day 7, where Day 1 is the day of each dose.

Table 4. Derived Variables for Presence of Each and Any Local Reaction Within 7 Days for Each Dose

Variable ^a	Yes (1)	No (0)	Missing (.)
Presence of each local reaction.	Participant reports the reaction as "yes" on any day (Day 1 through Day 7).	reaction as "no" on all	Participant does not report any data on all 7 days (Day 1 through Day 7) for the reaction.

Table 4.	Derived Variables for Presence of Each and Any Local Reaction Within
	7 Days for Each Dose

Variable ^a	Yes (1)	No (0)	Missing (.)
Presence of any local reaction.	Participant reports any local reaction as "yes" on any day (Day 1 through Day 7).	For all 3 local reactions, participant reports "no" on all 7 days (Day 1 through Day 7) or as a combination of "no" and missing on all 7 days (Day 1 through Day 7).	Participant does not report any data for all 3 local reactions on all 7 days (Day 1 through Day 7).

a. The variables will be derived for each and any of the local reactions (redness, swelling, and pain at the injection site) and for each and any of the severe local reactions within the interval from Day 1 through Day 7 after vaccination.

Severity and Maximum Severity

For each local reaction reported, the maximum severity grade will be derived for the e-diary collection period (Day 1 through Day 7, where Day 1 is the day of each dose) as follows:

Maximum severity grade = highest grade (maximum severity) within 7 days after vaccination (Day 1 through Day 7) among severity grades where the answers are neither "no" nor missing for at least 1 day during the interval from Day 1 through Day 7.

Duration (First to Last Day Reported)

For participants experiencing any local reactions (or those with a derived reaction as described in Table 4), the maximum duration (last day of reaction - first day of reaction + 1) will be derived for each study vaccination group. Resolution of the reaction is the last day on which the reaction is recorded in the e-diary or the date the reaction ends if it is unresolved during the participant e-diary recording period (end date collected on the CRF), unless chronicity is established. If there is no known end date, the duration will be considered unknown and set to missing. Participants with no reported reactions have no duration.

Onset Day

The onset day of each local reaction will be derived. Onset day is defined as the first day of reporting any severity.

For the onset day of each local reaction, if participants report a change in severity of the local reaction, only the first day of reporting that specific local reaction will be counted.

In summary, the following variables will be derived for local reactions:

- 1. Presence or absence of each local reaction on each day (Day 1-7) after vaccination.
- 2. Presence or absence of each local reaction on "any day (Day 1-7)" after vaccination.
- 3. Maximum severity of each local reaction on "any day (Day 1-7)" after vaccination.
- 4. Presence or absence of any local reaction on "any day (Day 1-7)" after vaccination.
- 5. Duration of each local reaction after vaccination.
- 6. Onset day of each local reaction after vaccination.
- 7. Onset day of any local reaction after vaccination.

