8.2.3. Electronic Diary

Participants will be required to complete a reactogenicity e-diary after each vaccination through an application installed on a provisioned device or on the participant's own personal device. All participants will be asked to monitor and record local reactions, systemic events, and use of antipyretic medication for 7 days from the day of administration of the study intervention. The reactogenicity e-diary allows recording of these assessments only within a fixed time window, thus providing the accurate representation of the participant's experience at that time. Data on local reactions and systemic events reported in the reactogenicity e-diary will be transferred electronically to a third-party vendor, where they will be available for review by investigators and the Pfizer clinicians at all times via an internet-based portal.

At intervals agreed to by the vendor and Pfizer, these data will be transferred electronically into Pfizer's database for analysis and reporting. These data do not need to be reported by the investigator in the CRF as AEs.

Investigators (or designee) will be required to review the reactogenicity e-diary data online at frequent intervals as part of the ongoing safety review.

The investigator or designee must obtain stop dates from the participant for any ongoing local reactions, systemic events, or use of antipyretic medication on the last day that the reactogenicity e-diary was completed. The stop dates should be documented in the source documents and the information entered in the CRF.

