Visit 206 is to be conducted within 26 to 30 days after Visit 201 or 203, depending on if the participant is assigned to a 1- or 2-visit vaccination schedule.

- Record AEs as described in Section 8.3.
- Record nonstudy vaccinations as described in Section 6.8.
- Record prohibited medication use as described in Section 6.8.1.
- Discuss contraceptive use as described in Section 10.4.
- Collect a blood sample of approximately 50 mL for immunogenicity testing, unless advised otherwise by the sponsor based on the vaccine group to which the participant is assigned.
- If the participant has consented to provide a blood sample for description of cell-mediated immune response, collect a blood sample (approximately 50 mL) for PBMC isolation, unless advised otherwise by the sponsor based on the vaccine group to which the participant is assigned.
- Review the participant's reactogenicity e-diary data. Collect stop dates of any reactogenicity e-diary events ongoing on the last day that the reactogenicity e-diary was completed and record stop dates in the CRF if required.
- If not already completed, collect the participant's e-diary or assist the participant with removing the study application from his or her own personal device.
- Record any AEs that occur within the 48 hours after the blood draw as described in Section 8.3.
- Ask the participant to contact the site staff or investigator if a medically attended event (eg, doctor's visit, emergency room visit) or hospitalization occurs.
- Complete the source documents.

• The investigator or an authorized designee completes the CRFs.

10.10.8.8.8. Visit 207 – 8-Week Follow-up Visit (After Vaccination 1 or 2) – 52 to 60 Days After Last Study Vaccination

Visit 207 is to be conducted within 52 to 60 days after Visit 201 or 203, depending on if the participant is assigned to a 1- or 2-visit vaccination schedule.

- Record AEs as described in Section 8.3.
- Record nonstudy vaccinations as described in Section 6.8.
- Record prohibited medication use as described in Section 6.8.1.
- Collect a blood sample of approximately 50 mL for immunogenicity testing, unless advised otherwise by the sponsor based on the vaccine group to which the participant is assigned.
- Record any AEs that occur within the 48 hours after the blood draw as described in Section 8.3.
- Ask the participant to contact the site staff or investigator if a medically attended event (eg, doctor's visit, emergency room visit) or hospitalization occurs.

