3.1.1.2. Systemic Events

During the reactogenicity e-diary reporting period, participants will be asked to assess vomiting, diarrhea, headache, fatigue, chills, new or worsened muscle pain, and new or worsened joint pain and to record the symptoms in the reactogenicity e-diary. The symptoms will be assessed by the participant as absent, mild, moderate, or severe according to the grading scale in Table 5.

Table 5. Systemic Event Grading Scale

	Mild (Grade 1)	Moderate (Grade 2)	Severe (Grade 3)	Potentially Life-Threatening (Grade 4)
Vomiting	1-2 times in 24 hours.	>2 times in 24 hours.	Requires IV hydration.	Emergency room visit or hospitalization for hypotensive shock.
Diarrhea	2 to 3 loose stools in 24 hours.	4 to 5 loose stools in 24 hours.	6 or more loose stools in 24 hours.	Emergency room visit or hospitalization for severe diarrhea.
Headache	Does not interfere with activity.	Some interference with activity.	Prevents daily routine activity.	Emergency room visit or hospitalization for severe headache.
Fatigue/tiredness	Does not interfere with activity.	Some interference with activity.	Prevents daily routine activity.	Emergency room visit or hospitalization for severe fatigue.
Chills	Does not interfere with activity.	Some interference with activity.	Prevents daily routine activity.	Emergency room visit or hospitalization for severe chills.
New or worsened muscle pain	Does not interfere with activity.	Some interference with activity.	Prevents daily routine activity.	Emergency room visit or hospitalization for severe new or worsened muscle pain.

Table 5.	Systemic Ev	vent Grading S	scale
	~,, > = = = = =	· • • • • • • • • • • • • • • • • • • •	

	Mild (Grade 1)	Moderate (Grade 2)	Severe (Grade 3)	Potentially Life-Threatening (Grade 4)
New or worsened joint pain	Does not interfere with activity.	Some interference with activity.	Prevents daily routine activity.	Emergency room visit or hospitalization for severe new or worsened joint pain.

Abbreviation: IV = intravenous.

The derivations for systemic events will be handled similarly to the way local reactions are handled for presence of event, severity level, duration, and onset day. The variables associated with the systemic events will be computed similarly to the way local reactions are computed (see Section 3.1.1.1).

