6.1.1.1.1. Main Analysis

- Estimand: The percentage of participants reporting local reactions (redness, swelling, and pain at the injection site) for up to 7 days following each vaccination (Section 3.1.1.1).
- Estimand strategy: Treatment policy (Section 2.2.1).
- Analysis set: Safety population for 1-visit schedules and Vaccination 1 safety population or Vaccination 2 safety population for 2-visit schedules (Section 4).
- Analysis time point: Day 1 through Day 7 after each vaccination. Refer to Section 3.1.1.1 for maximum severity.
- Analysis methodology: Descriptive summary statistics.
- Intercurrent events and missing data: The participants without any e-diary data throughout the 7 days after each vaccination will be excluded from the analysis at that particular vaccination. For participants who discontinue, all collected data will be included; intermediate missing values will not be imputed.
- Reporting results: The proportion, the numerator (n) and denominator (N) used for the calculation of the proportion, and associated 2-sided Clopper-Pearson 95% CI will be presented, by vaccine group, for the following variables:
 - o Presence or absence of each local reaction on each day (Day 1-7) after vaccination.
 - o Presence or absence of each local reaction on "any day (Day 1-7)" after vaccination.
 - o Presence or absence of any local reaction on "any day (Day 1-7)" after vaccination.
 - o Maximum severity of each local reaction on "any day (Day 1-7)" after vaccination.
- The n, mean, standard deviation, median, minimum, and maximum will be presented by vaccine group, for the following variables:
 - O Duration of each local reaction after vaccination.

- Onset day of each local reaction after vaccination.
- Onset day of any local reaction after vaccination.

Figures:

Bar charts with the proportions of participants for each local reaction throughout 7 days will be plotted by vaccine group. The bars will be divided into severity categories to highlight the proportions of participants by maximum severity.

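### Reactions with no obtainable end date are left out of the duration summaries instead of being kept as known minimums, so the mean and especially the maximum duration can be understated

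*SAP*

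**What the plan says.** SAP section 3.1.1.1 defines duration as last day minus first day plus 1. The last day is either the last diary day on which the reaction was recorded or, for a reaction that outlasts the diary, "the date the reaction ends if it is unresolved during the participant e-diary recording period (end date collected on the CRF". An exception follows, "unless chronicity is established", with no value or reporting rule for such cases. The next sentence reads: "If there is no known end date, the duration will be considered unknown and set to missing".

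SAP section 6.1.1.1.1 then lists "Duration of each local reaction after vaccination" among the variables summarised by vaccine group with n, mean, standard deviation, median, minimum and maximum. It asks for no count of reactions without an end date and no lower bound for them.

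The rule carries over. SAP section 3.1.1.2 states: "The derivations for systemic events will be handled similarly to the way local reactions are handled for presence of event, severity level, duration, and onset". SAP section 3.1.1.4 applies the local-reaction rules, where applicable, to the duration of antipyretic use.

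End dates are actively sought. SAP section 3.1.1.1 says: "If a local reaction persists beyond the end of the reactogenicity e-diary period following each vaccination, the participant will be requested to report that information". Protocol section 8.2.3 says: "The investigator or designee must obtain stop dates from the participant for any ongoing local reactions, systemic events, or use of antipyretic medication" still present on the last completed diary day. The Substudy B schedule of activities (Protocol section 10.10.1) lists this at Visits 202, 203, 205 and 206. The Visit 206 procedures (Protocol section 10.10.8.8.7, 26 to 30 days after the last vaccination) repeat it: "Collect stop dates of any reactogenicity e-diary events ongoing on the last day that the reactogenicity e-diary was completed". The procedures for Visits 207 and 208 do not list it.

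**The concern.** A reaction last seen ongoing, with no end date, does not have a wholly unknown duration. Its first day and the last day it was known to be present are on record, so it is right-censored with a known minimum. Setting it to missing discards that minimum.

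Three kinds of reaction fall under the rule: those judged chronic, those unresolved at the last visit that lists stop-date collection, and those ongoing when the participant was lost or withdrew. The first two are among the longest in the study, so for them the deletion depends on the outcome being measured.

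What is at stake is one descriptive part of the tolerability profile. Where such a reaction occurs, the reported maximum is the longest reaction that had an end date, and nothing in the planned table says that a longer one was left open. Initial-enrollment groups have 15 participants and are analysed separately from expanded enrollment (SAP sections 2.3.1 and 5.2), so one omitted record can decide a group's maximum.

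**Working it through.** The documents give no expected duration, no rate of unresolved reactions and no rate of missing end dates, so there is no planned figure to reproduce. The numbers below show direction and range only; all durations and rates in them are assumed.

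**1. What each case contributes under SAP section 3.1.1.1**

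| Reaction | Duration used |
|---|---|
| Ends within the diary | Full length |
| Outlasts the diary, end date on CRF | Full length |
| Chronic, no end date | Missing (the exception gives no value, so I read the next sentence as applying) |
| Unresolved at Visit 206, no later date obtained | Missing |
| Ongoing at last contact, participant lost | Missing |

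**2. One open reaction among eleven.** Assume ten reactions of 2 days and one still present at Visit 206.
- Visit 206 is 26 to 30 days after vaccination. With vaccination on Day 1, that is Day 27 to Day 31.
- For onset between Day 1 and Day 7, the known minimum lies between 27 − 7 + 1 = 21 and 31 − 1 + 1 = 31 days.
- Rule as written: mean = 20/10 = 2.0; median 2; maximum 2.
- Minimum kept: mean at least (20 + 21)/11 = 3.7 to (20 + 31)/11 = 4.6; median 2; maximum at least 21 to 31.

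**3. A larger group.** Assume 72 reactors (60% of 120) with durations of 1 day (25), 2 days (27), 3 days (12), 4 days (4), 5 days (1), and one each of 9, 12 and 20 days. The total is 25 + 54 + 36 + 16 + 5 + 41 = 177 days.

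| Case | Mean | Median | Maximum |
|---|---|---|---|
| All end dates known | 177/72 = 2.46 | 2 | 20 |
| Only the 20-day reaction undated | 157/71 = 2.21 | 2 | 12 |
| Only the 9-day reaction undated | 168/71 = 2.37 | 2 | 20 |
| One 2-day reaction undated (diary stopped early) | 175/71 = 2.46 | 2 | 20 |

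The last row is 2.465 against 2.458, a slight rise. The maximum moves only if the undated reaction is the longest.

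**4. Range over the missing-date rate.** Simulation of 4,000 replicates with 72 reactors: short reactions geometric with mean about 1.7 days, 5% lasting past Day 7 with mean about 12 days, and a varying share of those long reactions undated.

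| Long reactions undated | Mean, full data to rule as written | Maximum changed |
|---|---|---|
| 0% | no change | 0% |
| 10% | 2.18 to 2.13 | 9% |
| 50% | 2.18 to 1.92 | 47% |
| 100% | 2.18 to 1.66 | 97% |

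With half undated, a 2% tail gives 1.87 to 1.77 (maximum changed in 37%), and a 10% tail gives 2.70 to 2.22 (46%). With 9 reactors (60% of 15), a 5% tail and half undated, the mean goes from 2.18 to 1.93 and the maximum changes in 19%. The average median moves by at most 0.07 day in the 5% table above. Over all settings run, the largest shift is 0.19 day (72 reactors, 10% tail, every long reaction undated). The simulation removes only long reactions, so it does not show the offsetting effect of short undated ones.

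**The case against.** The strongest reply is that the plan already works to prevent missing end dates. Protocol section 8.2.3 makes stop-date collection mandatory and sets no time limit on it. The visit procedures repeat it, and the SAP uses the CRF date. If sites comply, few durations will be missing. The planned n for duration, set against the number reporting the reaction, would show the shortfall. Duration is descriptive, the study has no hypotheses, and the primary estimands do not use it.

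Most of this stands, and it is why the point is minor. It does not close the gap. A chronic or still-unresolved reaction has no end date for a diligent site to obtain. After Visit 206 no visit procedure prompts for one, and Protocol section 8.2.3 does not require diary reactions to be recorded as AEs. The difference between the two counts shows that values are missing, but not that the reactions were open or for how long.

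A reader might infer more than the documents support:
- *That every reaction outlasting the diary drops out.* It does not; a CRF end date keeps it at full length.
- *That the reported median is too short.* It is 2 days with or without the open case in steps 2 and 3, and hardly moves in step 4.
- *That a missing end date always means a long reaction.* A participant who stops the diary early with a mild reaction and gives no stop date can also fall under the rule.
- *That the bias is certain, or larger wherever reactions persist longer.* It depends on undated reactions. A group with many long but dated reactions has none.

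**Conclusion.** The point holds as a minor weakness in a descriptive summary. Where a reaction has no obtainable end date, the SAP discards a known minimum, and the reported mean and maximum can be too low. The maximum is the more exposed: one open reaction, if it is the longest, determines it. The size cannot be estimated from the documents. Under the assumed inputs with 72 reactors and a 5% tail, the effect on the mean runs from nothing (all dates obtained) to about half a day (2.18 − 1.66 = 0.52, with every long reaction undated).

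This rests on two readings. First, chronic reactions fall under the set-to-missing sentence, since the SAP gives them no other value. Second, undated reactions are mainly long or unresolved ones; if they are mainly short reactions with an abandoned diary, the mean could instead rise slightly. The percentages reporting each reaction and the maximum severity are unaffected.

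**What to change.** In SAP section 3.1.1.1, replace the set-to-missing sentence. A reaction without an end date should keep a lower-bound duration, equal to the last day known ongoing minus the first day plus 1, and be flagged as open-ended. State there how chronic reactions are recorded and shown.

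In SAP section 6.1.1.1.1:
- report by vaccine group and vaccination the number of reactions without an end date, with chronic cases identified separately;
- label a mean that includes lower bounds as a minimum;
- show the maximum as ≥ the last day known ongoing when an open-ended reaction is the longest.

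Carry the same rule to systemic events (SAP sections 3.1.1.2 and 6.1.1.2.1) and antipyretic use (SAP section 3.1.1.4). A Kaplan-Meier time-to-resolution summary is optional: the median barely changes, groups can be as small as 15, and the method assumes non-informative censoring.

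The cost is SAP wording and a small change to the duration table. No new data are needed, and no value changes where all end dates are known.
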